1.3.2. Schedule of Activities – Follow-up Phase

After study intervention completion (or early discontinuation), all participants will enter the 48-week follow-up phase (unless they withdraw consent). In the control arm (Arm 6), the study visit frequency in this follow-up phase is lower than in Arms 1 to 5. Note that the participants in Arms 1 to 6 completing NA treatment at Week 48 will also follow a more frequent visit schedule with a study visit at least once every 4 weeks. In case NA re-treatment criteria are met, participants will switch to less frequent follow-up, provided that their HBV DNA and ALT values are stable.

The follow-up phase will be extended to 48 weeks after the end of NA treatment for participants who stop NA treatment during the follow-up phase based on meeting the NA treatment completion criteria. The visit frequency of participants from Arm 6 who enter the extended follow-up phase will be increased to match that of participants that enter the extended follow-up coming from Arms 1 to 5. In case NA re-treatment criteria are met, participants will switch to less frequent follow-up, provided that their HBV DNA and ALT values are stable.

The visit frequency during the follow-up phase and the extended follow-up phase is provided below for all intervention arms.

Study Phase		Follow-up ^{a,b}														
Follow up (FU) Week (W)		FU W4	FU W6	FU W8	FU W12	FU W16	FU W20	FU W24	FU W28	FU W30	FU W32	FU W36	FU W40	FU W42	FU W44	FU W48 EOS
FU Study Day (Window)	15 +/ 4d	29 +/ 4d	43 +/ 4d	57 +/ 4d	85 +/ 4d	113 +/ 4d	141 +/ 4d	169 +/ 4d	197 +/ 4d	211 +/ 4d	225 +/ 4d	253 +/ 4d	281 +/ 4d	295 +/ 4d	309 +/ 4d	337 +/ 4d
Visits in Intervention Arms 1 to 6 (NA stopped) ^c	X	X	X	X	X	X	X	X	X		X	X	X		X	X
Visits in Intervention Arms 1 to 5 (NA continued)	X	X	X	X	X	X	X	X		X		X		X		X
Visits in Intervention Arm 6 (NA continued)					X			X				X				X
Extended Follow up (Ext FU) in participants who complete NA treatment during follow up ^d	Ext FU W2	Ext FU W4	Ext FU W6	Ext FU W8	Ext FU W12	Ext FU W16	Ext FU W20	Ext FU W24	Ext FU W28	Ext FU W30	Ext FU W32	Ext FU W36	Ext FU W40	Ext FU W42	Ext FU W44	Ext FU W48 EOS
Ext FU Study Day (Window)	15 +/ 4d	29 +/ 4d	43 +/ 4d	57 +/ 4d	85 +/ 4d	113 +/ 4d	141 +/ 4d	169 +/ 4d	197 +/ 4d	211 +/ 4d	225 +/ 4d	253 +/ 4d	281 +/ 4d	295 +/ 4d	309 +/ 4d	337 +/ 4d
Visits in Interventions Arms 1 to 6 (NA stopped)	X	X	X	X	X	X	X	X	X		X	X	X		X	X
Visits in Interventions Arms 1 to 6 (NA re-started)	X	X	X	X	X	X	X	X		X		X		X		X

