5.4.3.2. NA Treatment Completion Criteria During FU

The count and proportion of participants who met the NA treatment completion criteria (as defined in Section 5.2.1) at any time during the FU phase, regardless of the treatment duration, will be summarized by intervention arm. All of NA treatment completion criteria will be checked based on clinical laboratory tests in FU phase.

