5.4.3.3. Time to NA Treatment Completion

Time to meet NA completion criteria is defined as the number of days between the date of first study intervention intake and the date of meeting NA completion criteria regardless of whether the participant actually discontinued treatment (i.e. the date of meeting NA completion criteria – the date of first study intervention intake + 1). The participants who withdrew early from the study before meeting NA completion criteria or who did not meet NA completion criteria will be censored at the last available lab assessment with non-missing ALT, HBV DNA, HBeAg and HBsAg results.

Time to meet NA completion criteria will be summarized by intervention arm. The Kaplan-Meier method will be used to estimate and plot the cumulative incidence by each intervention arm. The log-rank test will be performed to compare among the intervention arms. The median time with 90% CI will be estimated using Kaplan-Meier method. In addition, the hazard ratio and the corresponding 90% confidence interval will be estimated based on a stratified Cox's regression model by the 2 randomization stratification factors

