5.4.14. Flares

5.4.14.1. Definition

The criteria based on blood markers/lab tests for each of the flare types are defined as below.

a) Virologic flare is defined as follows:

Virologic flare will be assessed only for those participants who are off-treatment and had HBV DNA < LLOQ at the last observed time point on all study treatments.

The start date of a confirmed virologic flare is defined as the first date of two consecutive visits with HBV DNA > 200 IU/mL. The end date of the same confirmed virologic flare is defined as the first date when HBV DNA value returns to \leq 200 IU/mL or the date of treatment restart, whichever comes first. Each virologic flare will be categorized based on the confirmed (i.e., two consecutive values) peak HBV DNA above any of the three thresholds within the start and end date of that flare as follows: 20,000 IU/mL 2,000 IU/mL and 200 IU/mL.

- 1 (Yes) = confirmed** HBV DNA > peak threshold.
- 0 (No) = at least one off-treatment HBV DNA measurement available and not meeting the criteria of confirmed HBV DNA > peak threshold.
- 2 (Not applicable) = no off-treatment HBV DNA quantitative measurements available.

b) Biochemical flare is defined as follows:

- 1 (Yes) = confirmed** ALT and/or AST \geq 3x ULN and \geq 3x nadir (ie, lowest value observed up to the start of the flare)
- 0 (No) = otherwise

The start date of a confirmed biochemical flare is defined as the first date of two consecutive visits with ALT and/or AST \geq 3x ULN and \geq 3x nadir. The end date of the same confirmed biochemical flare is defined as the first date when there is a 50% reduction from the peak ALT and/or AST level & $<$ 3x ULN.

c) Clinical flare is defined as follows:

Clinical flare will be assessed with both derivations specified above for virologic flare.

- 1 (Yes) = confirmed** HBV DNA > peak threshold and confirmed** ALT and/or AST \geq 3x ULN and \geq 3x nadir (ie, lowest value observed up to the start of the flare).
- 0 (No) = otherwise

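### While NA continues in follow-up, Arms 1–5 have 12 scheduled visits and Arm 6 has 4, and the comparisons with control on events first seen in that period make no allowance for it

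*Protocol*

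**What the plan says.** Protocol 1.3.2 says of the follow-up phase: "In the control arm (Arm 6), the study visit frequency in this follow-up phase is lower than in Arms 1 to 5". The table beneath gives different visit rows for participants who continue NA in Arms 1–5 and in Arm 6. Once NA is stopped, all six arms share one row, and for extended follow-up the protocol adds: "The visit frequency of participants from Arm 6 who enter the extended follow-up phase will be increased to match" that of participants coming from Arms 1–5. Under Protocol 6.6, the last test in follow-up that can lead to stopping NA is at Follow-up Week 42, or Week 36 in Arm 6.

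The analyses that draw on this period are:

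- **Completion criteria during follow-up.** SAP 5.4.3.2 counts participants who meet them "at any time during the FU phase, regardless of the treatment duration, will be summarized by intervention arm". The SAP only summarises here. The between-arm test, a stratified CMH test with 90% CIs, is in Protocol 9.4.1.3, which also lists flare frequency.
- **Time to completion.** SAP 5.4.3.3 uses Kaplan-Meier and a stratified Cox model, and states: "The log-rank test will be performed to compare among the intervention arms".
- **Time to HBsAg or HBeAg below LLOQ.** SAP 5.4.11 applies the same methods to the first occurrence, with censoring at the last available assessment.
- **Biochemical flares.** SAP 5.4.14.1 says: "The start date of a confirmed biochemical flare is defined as the first date of two consecutive visits" that meet the ALT/AST criterion. A criterion met at the last observed time point also counts as confirmed. Biochemical flares are counted both on and off treatment, and on-treatment includes time on NA alone. They feed the overall incidence of at least one flare of any type.

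SAP Table 2b gives Arm 6 participants who continue NA their own column with four windows. Neither document restricts these analyses to common visits, uses an interval-censored method, or plans a sensitivity analysis for unequal ascertainment.

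**The concern.** An any-time or first-occurrence endpoint can be met only when someone looks. If one arm is looked at three times as often, it will show more events and earlier event dates even when the true rates are equal. Here the extra looks fall in the active arms. They favour those arms on completion criteria and clearance, and count against them on flares.

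Most of the control arm is exposed to this. The protocol assumes a 5% control response at Week 48, so about 45 × 0.95 ≈ 43 of the 45 Arm 6 participants would continue NA on the sparse schedule, ignoring withdrawals. Protocol 4.2 keeps Arm 6 in the study for the full 96 weeks to support within-study efficacy measurements, so these comparisons are intended to be read.

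**Working it through.** **Inputs.** Visit weeks are from the follow-up table in Protocol 1.3.2, and the last qualifying tests from Protocol 6.6. Episode lengths, uniform onset and event rates are assumptions, because the documents give none.

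**1. Count of looks.**

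- Arms 1–5, NA continued: Follow-up Weeks 2, 4, 6, 8, 12, 16, 20, 24, 30, 36, 42, 48, which is 12 visits.
- Arm 6, NA continued: Weeks 12, 24, 36, 48, which is 4 visits. This agrees with the four windows in SAP Table 2b.
- Any arm, NA stopped: 14 visits.
- Tests that can lead to stopping NA: 11 (through Week 42) against 3 (through Week 36).

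The gaps between visits are four each of 2, 4 and 6 weeks in Arms 1–5, and four of 12 weeks in Arm 6.

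**2. Events that persist.** With onset uniform over 48 weeks, mean delay = Σ gap² / (2 × 48).

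- Arms 1–5: (4×4 + 4×16 + 4×36) / 96 = 224/96 = 2.3 weeks.
- Arm 6: (4×144) / 96 = 576/96 = 6.0 weeks.

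**3. Transient events seen at least once.** For an episode of length d, the probability is Σ min(gap, d) / 48.

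| Assumed length | Arms 1–5 | Arm 6 |
|---|---|---|
| 2 weeks | 24/48 = 50% | 8/48 = 17% |
| 4 weeks | 40/48 = 83% | 16/48 = 33% |
| 6 weeks | 48/48 = 100% | 24/48 = 50% |
| 8 weeks | 48/48 = 100% | 32/48 = 67% |
| 12 weeks | 100% | 100% |

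The result depends a little on how the end of follow-up is treated. If the whole episode must fit within the 48 weeks, the 4-week figures become 36/44 = 82% and 12/44 = 27%, and the 8-week figures 100% and 24/40 = 60%.

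**4. Seen at two consecutive scheduled visits.** The onset must fall in one gap and the episode must reach the visit after next, so the probability is Σ max(0, min(gap, d − next gap)) / 48. In Arms 1–5 an 8-week episode gives 28/48 = 58% and a 4-week episode 6/48 = 12.5%. In Arm 6 it is 0% for any length up to 12 weeks. This counts scheduled visits only.

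**5. Effect on a hazard ratio.** A simulation of follow-up alone used equal true hazards, 20,000 participants per schedule, and true 48-week incidence of 10% or 20%. The Cox HR for the Arms 1–5 schedule against the Arm 6 schedule was:

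- persistent events: 1.07 and 1.01;
- 8-week episodes: 1.54 and 1.62;
- 4-week episodes: 2.55 and 2.86.

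Endpoints timed from first dose also include 48 weeks on identical schedules, which would dilute these ratios.

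**6. After restriction to common visits.** Every arm has 4 looks (3 for qualifying to stop NA), a mean delay of 6.0 weeks, and the same detection probability for a given episode length. The schedule-driven difference in scheduled looks is then zero.

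**The case against.** The strongest reply has four parts.

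1. **The protocol supplements scheduled visits.** Unscheduled visits are allowed (Protocol 1.3.2, note a). An ALT/AST elevation of at least 3x ULN and 3x nadir triggers a confirmatory visit, preferably within 7 days, and then weekly monitoring (8.3.6.1). The last-observed-time-point rule lets a single final value count. This stands against reading 58% against 0% in step 4 as the real confirmation rates. It does not restore first detection: a silent elevation must be seen before it can trigger anything, and unscheduled visits are discretionary at a time when investigators know who is in the control arm (Protocol 6.3).
2. **Persistent events are found anyway.** This largely stands. An event lasting to a common visit is found late rather than missed, with an HR of about 1.0 to 1.1. The 11 against 3 figure counts looks and does not measure bias.
3. **A by-visit view already exists.** From Week 44, SAP 5.4.3.1 summarises by arm and time point who has not met the completion criteria, which includes visits common to all arms. This is useful, but it does not correct the any-time test or the time-to-event models.
4. **Moving every follow-up comparison to common visits would do harm.** This stands. It would discard off-treatment data collected on matched schedules. Two-visit flare confirmation would be 12 weeks apart in every arm. It would also lose participants in Arms 1–5 who stop NA at an intermediate visit, because SAP Table 1 then moves them to extended follow-up with a new day count.

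**Conclusion.** The point holds for a limited set of comparisons with Arm 6: completion criteria met during follow-up, time to completion, time to HBsAg or HBeAg clearance, and biochemical flares on NA, with the overall flare incidence that includes them. In these, part of any difference from control may be due to visit frequency. For persistent events that part is mainly delay (6.0 against 2.3 weeks). For transient events it is under-detection in Arm 6 (33% against 83% for 4 weeks, 67% against 100% for 8 weeks). The visit counts are exact; the detection figures rest on assumed lengths and uniform onset.

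A reader might infer more than the documents support:

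- **That the main endpoints are biased.** The primary endpoint uses Week 44 tests, before the schedules diverge, and the key secondary uses Week 72, a visit all arms have.
- **That all flare comparisons are biased.** Virologic and clinical flares are assessed only off treatment, where all arms share 14 visits. They are affected only indirectly, through the unequal chances to stop NA.
- **That time to on-treatment flare carries the full bias.** Non-events are censored at or before EOT, which is in the double-blind phase (SAP 5.4.14.2, Table 2a). The remaining flaw is that events on NA in follow-up still meet the on-treatment definition.
- **That efficacy is inflated in general.** For lasting responses the effect is small.

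These endpoints carry no multiplicity-controlled claim (SAP 5.1.1, 5.4), so the SAP should be changed, but the trial's main conclusions do not depend on it.

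**What to change.** For comparisons with Arm 6 that use NA-continued follow-up, add to the SAP a prespecified sensitivity analysis on Follow-up Weeks 12, 24, 36 and 48 (through Week 36 for qualifying to stop NA), and state that interpretation against control rests on it. Specify that:

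- clearance and completion events are dated to the next common visit, or interval-censored methods are used;
- participants in Arms 1–5 who qualified and stopped NA at an intermediate visit are shown both as met and as not met, so that true responders are not lost;
- a biochemical flare on NA must be first detected at a common visit, and triggered confirmatory repeats count towards confirmation in the same way in all arms;
- time to on-treatment flare counts events only up to EOT, to match the censoring.

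Leave the off-treatment flare analyses and the full-schedule by-arm summaries unchanged. No visit changes.

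The cost is SAP wording and one added set of derivations. The downside is that this comparison does not use the intermediate visits in Arms 1–5.

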The investigator should consider to re-start NA treatment per local standard of care at the EOS visit ([Extended] Follow-up Week 48) for participants who met the NA treatment completion criteria at Week 48 or during the follow-up phase, who did not re-start NA treatment during the follow-up phase, and who did not achieve and maintain HBsAg seroclearance. NA will not be provided by the sponsor after the final study visit.

If a participant prematurely discontinues investigational intervention (before Week 48), follow-up assessments should be obtained as per the Schedule of Activities until 48 weeks after the end of investigational intervention unless the participant withdraws consent. In this case, NA treatment may be continued or, in consultation with the sponsor, discontinued, based on the above-mentioned NA treatment completion criteria.

NA Re-treatment Criteria and Monitoring After Stopping of NA

Participants who meet the NA treatment completion criteria outlined above will be monitored closely during the follow-up phase.

After stopping NA treatment, participants should be monitored as follows:

- Regular monitoring visits will be every 4 weeks during the follow-up phase in accordance with the Schedule of Activities.
- A post-treatment HBV DNA value of >20,000 IU/mL should trigger re-testing of ALT/AST, HBV DNA, and total and direct bilirubin within a maximum of 7 days from receipt of the data and further repeats as necessary (ie, weekly until HBV DNA returns to <20,000 IU/mL).
- A post-treatment HBV DNA value of >2,000 IU/mL (but <20,000 IU/mL) should trigger a re-test within 14 days from receipt of the data and further repeats as necessary (ie, every other week until HBV DNA returns to <2,000 IU/mL).
- A post-treatment ALT value of >5x ULN should trigger re-testing of ALT, AST, ALP, total and direct bilirubin, International Normalized Ratio (INR), albumin, and HBV DNA on a weekly basis until ALT and AST levels have returned to <5x ULN.

After stopping NA treatment, participants should re-start NA treatment:

- Immediately with signs of decreasing liver function based on laboratory findings (eg, INR, direct bilirubin) or clinical assessment (eg, ascites, hepatic encephalopathy).
- Immediately with an HBV DNA value of >100,000 IU/mL (irrespective of confirmation and/or ALT increase).
- With confirmed post-treatment HBeAg seroreversion (HBeAg positive after it was negative at NA completion).

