- With confirmed* post-treatment increases in HBV DNA >2,000 IU/mL and ALT >5x ULN.
- With confirmed* post-treatment increases in HBV DNA >20,000 IU/mL.

Note: Additional re-testing and/or earlier restarting of NA treatment is at the investigator's discretion, even if the above cut-offs are not yet met.

To avoid delays in decision making, sites are encouraged to run local re-testing in parallel with central retesting in the situations described above that require more frequent re-testing. Local test results are to be recorded in the CRF and/or source documents, including information on the HBV DNA assay used. In

^{*} At least 4 weeks apart – frequency of visits as described above

addition, to avoid delays in NA re-treatment, it should be considered to dispense NA to participants who potentially met the NA re-treatment criteria (eg, pending confirmation) and who will not be available to come to the study site immediately at the time the confirmatory test results will become available. This should ensure that the participant can immediately re-start NA treatment if indicated, upon direct confirmation by the investigator.

In case NA treatment is re-started, participants will be followed until the end of the study or until clinical stabilization, whichever comes later.

Management of intervention-emergent ALT/aspartate aminotransferase (AST) elevations is discussed below.

NUMBER OF PARTICIPANTS

A target of 450 male and female participants will be randomized.

Description of Interventions

Intervention name	JNJ-3989	Placebo for JNJ-3989	JNJ-6379	Placebo for JNJ-6379	Entecavir (ETV) monohydrate	Tenofovir disoproxil fumarate (TDF)	Tenofovir alafenamide (TAF)***
Dosage formulation	Solution for injection	Solution for injection	Tablets	Tablets	Film-coated tablets	Film-coated tablets	Film-coated tablets
Unit dose strength(s)	200 mg/vial	0.9% saline	25 and 100 mg		0.5 mg	300 mg**	25 mg
Dosage regimen	100 mg once every 4 weeks (Arms 1 and 3) 200 mg once every 4 weeks (Arm 2) 40 mg once every 4 weeks (Arm 4)	0.5 mL once every 4 weeks (Arms 5 and 6)	250 mg qd (Arms 1 and 5)	qd (Arms 2, 3, 4, and 6)	Nucleoside-naïve patients: 0.5 mg qd Lamivudine- refractory patients: 1 mg* qd (but should preferably be treated with TDF or TAF instead)	300 mg qd	25 mg qd
Route of administration	Subcutaneous injection (in the abdomen)	Subcutaneous injection (in the abdomen)	Oral	Oral	Oral	Oral	Oral

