Study Intervention Administration																
Administer/Dispense NA ^e	(X)	(X)	(X)	(X)	(X)	(X)	(X)	(X)	(X)	(X)	(X)	(X)	(X)	(X)	(X)	(X)w
Oral study intervention accountability ^f		(X)	(X)	(X)	(X)	(X)	(X)	(X)	(X)	(X)	(X)	(X)	(X)	(X)	(X)	(X)
Assess NA treatment completion or NA re treatment criteria, as applicable	X	X	X	X	X	X	X	X	X	X	X	X	X	X	X	X

CONFIDENTIAL – FOIA Exemptions Apply in U.S.

Study Phase								Follo	w-up ^{a,b}							
Follow up (FU) Week (W)	FU W2	FU W4	FU W6	FU W8	FU W12	FU W16	FU W20	FU W24	FU W28	FU W30	FU W32	FU W36	FU W40	FU W42	FU W44	FU W48 EOS
FU Study Day (Window)		29 +/ 4d	43 +/ 4d	57 +/ 4d	85 +/ 4d	113 +/ 4d	141 +/ 4d	169 +/ 4d	197 +/ 4d	211 +/ 4d	225 +/ 4d	253 +/ 4d	281 +/ 4d	295 +/ 4d	309 +/ 4d	337 +/ 4d
Visits in Intervention Arms 1 to 6 (NA stopped) ^c	X	X	X	X	X	X	X	X	X		X	X	X		X	X
Visits in Intervention Arms 1 to 5 (NA continued)	X	X	X	X	X	X	X	X		X		X		X		X
Visits in Intervention Arm 6 (NA continued)					X			X				X				X
Extended Follow up (Ext FU) in participants who complete NA treatment during follow up ^d	Ext FU W2	Ext FU W4	Ext FU W6	Ext FU W8	Ext FU W12	Ext FU W16	Ext FU W20	Ext FU W24	Ext FU W28	Ext FU W30	Ext FU W32	Ext FU W36	Ext FU W40	Ext FU W42	Ext FU W44	Ext FU W48 EOS
Ext FU Study Day (Window)	15 +/ 4d	29 +/ 4d	43 +/ 4d	57 +/ 4d	85 +/ 4d	113 +/ 4d	141 +/ 4d	169 +/ 4d	197 +/ 4d	211 +/ 4d	225 +/ 4d	253 +/ 4d	281 +/ 4d	295 +/ 4d	309 +/ 4d	337 +/ 4d
Visits in Interventions Arms 1 to 6 (NA stopped)	X	X	X	X	X	X	X	X	X		X	X	X		X	X
Visits in Interventions Arms 1 to 6 (NA re-started)	X	X	X	X	X	X	X	X		X		X		X		X
Safety Evaluations																
Symptom directed physical examination ^g	X	X	X	X	X	X	X	X	X	X	X	X	X	X	X	X
Vital signs ^h	X	X	X	X	X	X	X	X	X	X	X	X	X	X	X	X
Triplicate 12 lead ECGi		X														
Liver ultrasound ^v								X								X
Clinical Laboratory Tests																
Hematology	X	X		X		X		X				X				X
Blood chemistry (including liver function tests) ^{j,k,l}	X	X	X ^m	X ^m	X	X ^m	X ^m	X	X ^m	X ^m	X ^m	X	X ^m	X	X	X
Blood coagulation	X	X			X			X				X		X		X
Urinalysis and urine chemistry ⁿ		X														
Urine pregnancy test (women of childbearing potential only)		X	 	X	X	X	X	X ^o	X ^o	Xº	X ^o	X				
AFP ¹								X								X
Efficacy Evaluations																
Fibroscan ^p								X								X
HBV Virology									37		37		37		37	
Blood sampling for HBV DNA and HBV RNA ^{q,x}	X	X	X	X	X	X	X	X	X	X	X	X	X	X	X	X
Sampling for viral genome sequencing ^r		X			X		X					X				X
HBV Serology																

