- e. No JNJ-3989/JNJ-6379/placebo will be administered or dispensed during follow-up. Administration/Dispensation of NA is only applicable for participants who did not meet the NA treatment completion criteria yet, or for those who met the NA re-treatment criteria. In between study visits, participants will take NA at home and they will bring their NA treatment with them to each study visit. At study visits, the NA treatment should be taken on site.
- f. For participants who take NA during follow-up.
- g. Symptom-directed physical examination, including body weight.
- h. Vital signs include supine SBP, DBP, pulse rate, and body temperature.
- i. All ECGs will be read centrally.
- j. Biochemistry samples must be taken after fasting for at least 10 hours for measurement of phosphate, calcium, creatinine, and lipids.
- k. Creatinine clearance (eGFR calculated by the CKD-EPI formula) will be assessed.
- 1. ALT/AST elevations (ie, ALT and/or AST ≥3x ULN and ≥3x nadir [ie, lowest value during study participation]), should trigger an assessment of confounding factors (alcohol intake, change in concomitant medication, and comorbidities) and a confirmatory visit, to be scheduled preferably within 7 days of the receipt of the initial ALT/AST results, to repeat laboratory testing of AFP, ALT, AST, ALP, bilirubin (total and direct), INR albumin, and HBV DNA. Additional tests should be considered based on clinical judgement. For more details and further management guidance refer to Section 8.3.6.1 Intervention-emergent ALT/AST Elevations and Section 10.6 Appendix 6: Intervention-emergent ALT/AST Elevations.
- m. Liver function tests only.

- n. Urine chemistry sample (quantitative measurement): creatinine, sodium, phosphate, glucose, protein, and albumin.
 Urinalysis by dipstick: specific gravity, pH, glucose, protein, blood, ketones, bilirubin, urobilinogen, nitrite, leukocyte esterase, and microscopic analysis if needed.
 In case of a positive dipstick result, a urine sample will be set aside for additional examination of the positive parameter at the central laboratory (eg, quantification as applicable).
- o. Urine pregnancy tests for at-home use will be provided to the participants from (Extended) Follow-up Week 24 onwards as urine pregnancy test should be done at least every 4 weeks. Results will be reported at the next visit. If a urine pregnancy test is positive, the investigator needs to be informed immediately by the participant.

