6.7. NA Re-treatment Criteria and Monitoring After Stopping of NA

Participants who meet the NA treatment completion criteria outlined in Section 6.6 will be monitored closely during the follow-up phase.

After stopping NA treatment, participants should be monitored as follows:

- Regular monitoring visits will be every 4 weeks during the follow-up phase in accordance with the Schedule of Activities.
- A post-treatment HBV DNA value of >20,000 IU/mL should trigger re-testing of ALT/AST, HBV DNA, and total and direct bilirubin within a maximum of 7 days from receipt of the data and further repeats as necessary (ie, weekly until HBV DNA returns to <20,000 IU/mL).
- A post-treatment HBV DNA value of >2,000 IU/mL (but <20,000 IU/mL) should trigger a re-test within 14 days from receipt of the data and further repeats as necessary (ie, every other week until HBV DNA returns to <2,000 IU/mL).
- A post-treatment ALT value of >5x ULN should trigger re-testing of ALT, AST, ALP, total and direct bilirubin, INR, albumin, and HBV DNA on a weekly basis until ALT and AST levels have returned to <5x ULN.

After stopping NA treatment, participants should re-start NA treatment:

- Immediately with signs of decreasing liver function based on laboratory findings (eg, INR, direct bilirubin) or clinical assessment (eg, ascites, hepatic encephalopathy).
- Immediately with an HBV DNA value of >100,000 IU/mL (irrespective of confirmation and/or ALT increase).
- With confirmed post-treatment HBeAg seroreversion (HBeAg positive after it was negative at NA completion).
- With confirmed* post-treatment increases in HBV DNA >2,000 IU/mL and ALT >5x ULN.
- With confirmed* post-treatment increases in HBV DNA >20,000 IU/mL.

Note: Additional re-testing and/or earlier restarting of NA treatment is at the investigator's discretion, even if the above cut-offs are not yet met.

To avoid delays in decision making, sites are encouraged to run local re-testing in parallel with central re-testing in the situations described above that require more frequent re-testing. Local test results are to be recorded in the CRF and/or source documents, including information on the HBV DNA assay used. In addition, to avoid delays in NA re-treatment, it should be considered to dispense NA to participants who potentially met the NA re-treatment criteria (eg, pending confirmation) and who will not be available to come to the study site immediately at the time the

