Screening Tests	• Urine pregnancy testing for women of indicated in the Schedule of Activities.	of childbearing potential at the time points		
	• Follicle-stimulating hormone (FSH) testing for postmenopausal women at screening.			
	• Testing for hepatitis A, B, C, D, and E virus and HIV-1 and -2 at screening.			
	• Testing for HBsAg, HBeAg, HBcrAg, and anti-HBs and anti-HBe antibodies at the time points indicated in the Schedule of Activities.			
	• Determination of coagulation parameters will be performed at the time points indicated in the Schedule of Activities. INR will be calculated by the central laboratory.			
	Alpha-fetoprotein at screening.			
Other optional tests in	Testing for HIV-1 and -2, and hepatitis A, C Testing for CMV, HSV, EBV infection	C, and E		
response to	Ig-Electrophoresis			
ALT flare	_ ^			
(refer to				
Section 10.6				

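### Footnote e of the follow-up Schedule conflicts with Sections 1.1, 4.2 and 6.7 on dispensing NA before re-treatment criteria are confirmed; the coagulation row is a lesser mismatch

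*Protocol*

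**What the plan says.** **Dispensing.** The follow-up Schedule (Protocol 1.3.2) has a row for administering or dispensing NA, and footnote e governs it. On who may be given the drug it reads: "NA is only applicable for participants who did not meet the NA treatment completion criteria yet, or for those who met the NA re-treatment criteria". That gives two groups, and the word *only* closes the list.

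The Synopsis (1.1) says "it should be considered to dispense NA to participants who potentially met the NA re-treatment criteria (eg, pending confirmation" and limits this to participants who could not get to the site straight away once the confirmatory result is known. The stated aim is to avoid delay in re-treatment. Sections 4.2 and 6.7 repeat this. NA supplied in this way is to be started only if indicated and once the investigator has confirmed it. Section 6.7 adds: "Additional re-testing and/or earlier restarting of NA treatment is at the investigator's discretion, even if the above cut-offs are not yet met".

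**Laboratory triggers.** Among the reasons to re-start NA, Section 6.7 lists: "Immediately with signs of decreasing liver function based on laboratory findings (eg, INR, direct bilirubin) or clinical assessment". The Schedule marks assessment of completion or re-treatment criteria in all 16 follow-up columns. INR belongs to the coagulation panel, for which Appendix 2 (10.2) says "Determination of coagulation parameters will be performed at the time points indicated in the Schedule of Activities". In the follow-up Schedule the "Blood coagulation" row is marked at Follow-up Weeks 2, 4, 12, 24, 36, 42 and 48.

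**The concern.** Section 2.3.3 records that post-treatment monitoring and the re-treatment criteria were updated after a case of HBV reactivation with subacute hepatic failure. Supplying NA in advance is one of the protocol's own measures against late re-start. Sites work from the Schedule visit by visit, and there the dispensing row carries a footnote that leaves that measure out. A participant who has stopped NA and is awaiting a confirmatory result is in neither of footnote e's groups. Nor is one whom the investigator re-starts below the cut-offs.

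The coagulation row raises a smaller question of the same kind. If re-treatment criteria are to be judged at every visit and INR is one of the findings named, one would expect either INR at those visits or an explanation of why other tests suffice. The Schedule gives neither.

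**Working it through.** The plan states no figure here to reproduce. The first part is a comparison of text and the second a count.

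**1. Dispensing, by state of a participant who has stopped NA**

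| State | Footnote e, read literally | Sections 1.1, 4.2 and 6.7 | Agree? |
|---|---|---|---|
| Immediate trigger (declining liver function, or HBV DNA >100,000 IU/mL) | Criteria met, NA allowed | Re-start at once | Yes |
| Criterion confirmed | Criteria met, NA allowed | Re-start | Yes |
| Confirmation pending, can attend promptly | Not allowed | Advance supply not aimed at this group | Yes |
| Confirmation pending, cannot attend promptly | Not allowed | Consider advance supply | **No** |
| Re-started at discretion below the cut-offs | Not allowed | Allowed | **No** |

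Footnote x sends the reader to Section 6.7 and Appendix 14 for re-start. It is attached to the HBV DNA and RNA sampling row, not to the dispensing row, and it does not mention advance supply. It softens the conflict without removing it.

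**2. What delay footnote e itself can cause**

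Under either text, a participant with a confirmation-based criterion starts NA only after confirmation, unless the investigator acts earlier. For the two HBV DNA-based criteria the confirming tests must be at least 4 weeks apart; Section 6.7 sets that interval. Once the result is confirmed, footnote e allows dispensing. So, leaving discretionary re-start aside:

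delay due to footnote e = date NA is collected − date of the confirmed result

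This is zero for anyone who can attend at once. The documents give no value for the others.

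**3. Coagulation count**

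- Off-NA visits: Weeks 2, 4, 6, 8, 12, 16, 20, 24, 28, 32, 36, 40, 44, 48 = 14.
- Coagulation marks: Weeks 2, 4, 12, 24, 36, 42, 48 = 7.
- In both lists: Weeks 2, 4, 12, 24, 36, 48 = 6.
- Off-NA visits without coagulation: 14 − 6 = 8 (Weeks 6, 8, 16, 20, 28, 32, 40, 44).
- Gaps between scheduled off-NA coagulation tests: 4−2 = 2, 12−4 = 8, 24−12 = 12, 36−24 = 12 and 48−36 = 12 weeks.
- Arms 1 to 5 continuing NA have 12 visits (Weeks 2, 4, 6, 8, 12, 16, 20, 24, 30, 36, 42, 48), and all 7 coagulation marks fall on them.

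The Week 42 mark falls at a visit that only participants on NA attend. Weeks 28, 32, 40 and 44, which only participants off NA attend, have no mark. Extended follow-up uses the same columns.

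**4. What else is scheduled at the 14 off-NA visits**

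- Liver function tests: 14 of 14.
- Symptom-directed examination: 14 of 14.
- INR when ALT and/or AST is ≥3x ULN and ≥3x nadir (footnote l), at a confirmatory visit preferably within 7 days.
- INR weekly when ALT exceeds 5x ULN (Section 6.7).
- The re-test prompted by HBV DNA >20,000 IU/mL covers ALT/AST, HBV DNA and bilirubin, but does not list INR.
- Unscheduled visits at the investigator's discretion (footnote a).

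**The case against.** The strongest reply is that the conflict is narrow. The advance-supply text is advisory and covers only participants who cannot attend promptly. The most urgent triggers need no confirmation, so those participants already count as having met the criteria under footnote e. Discretionary re-start is a note within Section 6.7, to which footnote x points, so few investigators would read footnote e as forbidding it. All of this limits the reach of the point. It does not reconcile the texts, because the wording of footnote e still excludes a step that three other sections ask sites to consider.

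A reader might infer that footnote e holds back NA for at least 4 weeks. The documents do not support that: the interval is Section 6.7's own confirmation rule and would apply whatever footnote e said.

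A reader might also infer that the coagulation row contradicts the re-treatment criteria. It does not. INR is one example beside direct bilirubin and clinical signs, and no passage requires it at each visit. Liver function tests and an examination are scheduled at all 14 visits, and rises in ALT or AST bring INR in. To miss a signal for want of scheduled INR would take an isolated INR change, with no qualifying enzyme rise, bilirubin change or clinical sign, at one of the 8 visits, and no discretionary re-test.

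**Conclusion.** The conflict between footnote e and Sections 1.1, 4.2 and 6.7 is real and bears on participant safety. It affects two groups: participants pending confirmation who cannot return promptly, and participants re-started at discretion. For the first, the delay attributable to footnote e is the time from the confirmed result to collecting NA, which cannot be quantified from the documents. This assumes that a site applies the footnote literally; a site that follows Section 6.7 would see no delay.

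The coagulation finding is a mismatch of secondary weight: 6 of 14 off-NA visits, with gaps of up to 12 weeks, and a Week 42 mark that no off-NA participant can use. It rests on reading the Schedule rows as printed. The statement that the criterion can still be assessed at every visit assumes that the liver function tests at the reduced visits include direct bilirubin. Footnote m does not list the tests, though the Appendix 2 chemistry list includes conjugated bilirubin.

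**What to change.** Reconcile footnote e of Section 1.3.2 with the advance-supply and discretionary re-start text in Sections 1.1, 4.2 and 6.7, so that a site reading any one of them reaches the same answer. The sponsor's medical team decides which text governs. The cost is the wording of one footnote or of the matching paragraphs.

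Separately, the sponsor should check that the coagulation row, including the Week 42 mark and its counterpart in extended follow-up, matches the off-NA visit schedule as intended. If it does, a short statement of how the laboratory criterion is assessed at visits without INR would close the question. If it does not, the cost is a table correction and possibly a further assay at visits where blood is already drawn. No testing frequency is proposed here.
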